4.3.3 Standard-of-Care Therapy

All patients will continue the required COPD inhaler therapy for this study that includes bronchodilator medication consisting of LABA and/or LAMA with or without ICS therapy. Refer to the local prescribing information for the formulation, packaging, and handling of these medications. Patients may not be on systemic (oral, IV, or IM) corticosteroids, biologics, or experimental therapeutics for the treatment of COPD. All patients will be provided with a diary to track daily study treatment and the date of any AEx events.

4.3.4 Medical Devices

In this study, the hyperpolarizer and the MRI machines are considered medical devices. Both devices are provided by the site and are not manufactured by or for the Sponsor. The hyperpolarizer and MRI machines are to be operated according to standard institutional practices.

4.4 CONCOMITANT THERAPY AND ADDITIONAL RESTRICTIONS

Concomitant therapy consists of any medication (e.g., prescription drugs, over-the-counter drugs, vaccines, herbal or homeopathic remedies, nutritional supplements) used by a patient in addition to protocol-mandated treatment from 7 days prior to screening (for medications not intended for the treatment of COPD) or 12 weeks prior to screening (for medications intended for the treatment of COPD) to the study completion/discontinuation visit. All such medications should be reported to the investigator and recorded on the Concomitant Medications electronic Case Report Form (eCRF).

Medications known to interact with azithromycin (see prescribing information or summary of product characteristics), in addition to digoxin and cyclosporine, should be used with caution.

Azithromycin should not be taken concurrently with ergot derivatives or simultaneously with antacids.

4.4.1 Permitted Therapy

All patients will continue their COPD therapy as recommended in published COPD guidelines (GOLD 2019 or BTS [NICE 2018]) and adhere to the following:

- Patients must be on stable therapy for at least 12 weeks prior to screening (Visit 1). There should be no anticipated changes in bronchodilator medication during the study.

Patients are permitted to use the following therapies during the study:

- Inhaled bronchodilator and ICS therapy
 - Patients may be on more than one bronchodilator with or without ICS therapy.
- Required COPD inhaler therapy for this study: Bronchodilator medication consisting of LABA and/or LAMA
- Additional background COPD therapy during the trial (e.g., phosphodiesterase-4 inhibitors and theophylline), but should remain stable from the start of screening (Visit 1) through completion of the study

From the start of screening (Visit 1) through completion of the study, the doses of bronchodilator medications and ICSs should remain stable. If changes to the background COPD medications are unavoidable, the patient may be switched to another brand or formulation that is equivalent to the medication that the patient was receiving at study entry. All changes to a patient's background medications should be documented in the COPD Targeted Concomitant Medications eCRF.

Rescue Therapy

It is expected that patients will be using short-acting anticholinergic and/or short-acting β -agonist therapy for acute COPD symptoms per existing treatment guidelines.

Combination inhalers (e.g., albuterol/ipratropium) are permitted. Short-acting bronchodilators must be administered via the patient's prescribed inhaler or nebulizer. Any short-acting bronchodilator that is prescribed as COPD rescue medication over the course of the study should be documented in the Concomitant Medications eCRF.

- Systemic corticosteroid use:

Patients who require any systemic corticosteroids within 4 weeks (oral or IV) or 12 weeks (IM) prior to screening will not be eligible for the trial (see Section 4.1.2).

The use of systemic corticosteroids is permitted for acute COPD management after randomization. Corticosteroids used for treatment of COPD (e.g., an AEx event as defined in Section 4.5.13) should be documented on the appropriate eCRF. Systemic corticosteroids should not be used other than for COPD exacerbations, but in the event that they are used to treat other medical conditions, this should be documented on the Concomitant Medications eCRF.

4.4.2 Prohibited Therapy

Use of the following concomitant therapies is prohibited as described below:

Medication	Restrictions ^a
COPD Therapies	
Systemic corticosteroids > 10 mg/QD (oral, IV, or IM)	Prohibited within 4 weeks (oral or IV) or 12 weeks (IM) prior to screening and during the screening period Prohibited for treatment of any condition other than COPD exacerbations or life-threatening conditions (e.g., spinal cord compression, cerebral edema) during the study period
Intra-articular corticosteroids > 10 mg	Prohibited within 4 weeks prior to screening, during the screening period, or during the treatment period
Maintenance oral or inhaled antibiotics	Prohibited within 2 weeks prior to screening, during the screening period, or during the treatment period
Investigational therapy (other than protocol-mandated study treatment)	Prohibited within 30 days or 5 half-lives, whichever is longer, prior to initiation of study treatment and during study treatment

IM=intramuscular; IV=intravenous; QD=once a day.

^a The Medical Monitor should be consulted in cases of uncertainty.

4.5 STUDY ASSESSMENTS

The schedule of activities to be performed during the study is provided in [Appendix 1](#). All activities should be performed and documented for each patient. Patients will be closely monitored for safety and tolerability throughout the study.

4.5.1 Informed Consent Forms and Screening Log

Written informed consent for participation in the study must be obtained before performing any study-related procedures (including screening evaluations). Informed Consent Forms for enrolled patients and for patients who are not subsequently enrolled will be maintained at the study site.

All screening evaluations must be completed and reviewed to confirm that patients meet all eligibility criteria before enrollment. The investigator will maintain a screening log to record details of all patients screened and to confirm eligibility or record reasons for screening failure, as applicable.

4.5.2 Medical History, Baseline Conditions, Concomitant Medications, and Demographic Data

Medical history, including clinically significant diseases, surgeries, cancer history (including prior cancer therapies and procedures), reproductive status, medication allergies, smoking history, and use of alcohol and drugs of abuse will be recorded at screening. In particular, sites should record whether the patient has any history of anaphylaxis, cancer, cardiovascular disease, eosinophilic disease, inflammatory or autoimmune disease, and surgeries with metal implants. Any history of smoking should be entered on the Tobacco Use History eCRF.

Demographic data will include age (date of birth), sex, and self-reported race/ethnicity.

4.5.3 Physical Examinations

A complete physical examination, performed at screening and other specified visits, should include an evaluation of the head, eyes, ears, nose, and throat, and the cardiovascular, dermatologic, musculoskeletal, respiratory, gastrointestinal, genitourinary, and neurological systems. Any abnormality identified at baseline should be recorded on the General Medical History and Baseline Conditions eCRF.

Limited, symptom-directed physical examinations should be performed at specified visits during the treatment period and as clinically indicated. Limited physical examination includes head, ears, eyes, nose, throat, cardiovascular, respiratory, and dermatologic examinations. Changes from baseline abnormalities should be recorded in patient notes. New or worsened clinically significant abnormalities should be recorded as adverse events on the Adverse Event eCRF.

4.5.4 Vital Signs

Vital signs will include measurements of respiratory rate, pulse rate, systolic and diastolic blood pressure while the patient is in a seated position (resting for at least 5 minutes), temperature, and oxygen saturation. Record abnormalities observed at baseline on the General Medical History and Baseline Conditions eCRF. At subsequent visits, record new or worsened clinically significant abnormalities on the Adverse Event eCRF.

4.5.5 Hearing Assessment

Patients in Cohort A will complete the *HHIE-S* ([Appendix 7](#)) and be queried on any onset hearing loss, worsening hearing loss, or hearing disturbances at specified timepoints.

Any patient in Cohort A randomized to azithromycin reporting onset or worsening hearing loss, reporting hearing disturbances, or demonstrating any decline in the interpretation of the HHIE-S score during the study will permanently discontinue azithromycin and be referred for formal audiology testing. Any patient who permanently discontinues azithromycin should be asked to continue all other study assessments, with the exception of azithromycin administration, through the end of the study.

4.5.6 Tobacco Use

At each study visit, the patient will be asked about their tobacco use. Any changes in tobacco use since screening (Visit 1) will be recorded in the eCRF.

4.5.7 Height and Weight

Height and weight will be measured at visits according to the schedule of activities (see [Appendix 1](#)). Weight will be determined to the nearest 0.1 kg. For body weight measurements, the patient will wear street clothes without any shoes, outerwear, or accessories.

4.5.8 Chest X-Rays

A chest X-ray must be performed during screening (between Visit 1 and Visit 2), unless a chest X-ray or CT scan has been obtained within 6 months prior to screening (Visit 1) and is available for review by the investigator. The X-ray may be performed locally, but must be reviewed by the investigator prior to randomization at Visit 2.

4.5.9 Spirometry and Forced Oscillometry

Spirometry, including the procedure for bronchodilator testing, which is based on the American Thoracic Society (ATS) and the European Respiratory Society (ERS) Consensus Statement (Graham et al. 2019) and forced oscillometry technique (FOT), will be conducted as per the study pulmonary function manual. Spirometry measures will include pre- and post-bronchodilator FEV₁ and FVC (volume in liters) per [Appendix 1](#). The percentage of predicted FEV₁ and percentage of predicted FVC will

be derived from these volume measurements using the equations derived from the third National Health and Nutrition Examinations Survey (Hankinson et al. 1999). Inhaled bronchodilator therapies that may affect spirometry must be withheld until pre-bronchodilator spirometry measurements are completed. Patients must be made aware that inhaled bronchodilator use is prohibited within a specified window prior to each clinic visit, with the exception of the screening visit (Visit 1), as follows:

- Twice-daily LABA and twice-daily LAMA: within 12 hours prior to spirometry
- Once-daily LABA and once-daily LAMA: within 24 hours prior to spirometry
- Short-acting β -agonist/ipratropium: within 4 hours prior to spirometry

Pre-bronchodilator spirometry should not be performed during the screening visit (Visit 1) if the patient did not withhold bronchodilator medications during the specified time period prior to the screening assessment. The remaining screening assessments should be completed as indicated in [Appendix 1](#).

FOT will be conducted as per the study pulmonary function manual, which is based on the ERS Task Force on Respiratory Impedance Measurements (Oostveen et al. 2003). FOT measures will include resistance at low frequency, 5 Hz (R_5), resistance change (R_{5-20}), AX, and reactance difference inspiration – expiration (ΔX_5).

FOT assessments should be performed shortly before completing the pulmonary function testing assessments.

4.5.10 Gas Exchange-Diffusion Capacity of the Lung for Carbon Monoxide Assessment

DL_{CO} will be conducted as per the study pulmonary function manual, which is based on the 2017 ATS/ERS guidance (Graham et al. 2017).

4.5.11 High-Resolution Computed Tomography

Good-quality pulmonary quantitative HRCT scans (one at full inspiration and one at expiration) performed per the imaging acquisition guidelines provided in the study-specific imaging manual will be obtained at baseline. Alternatively, an acceptable set of scans performed ≤ 6 months prior to screening and in accordance with study image acquisition guidelines can be used for eligibility determination.

Follow-up HRCT scans will be performed at specified timepoints (see [Appendix 1](#)). Ideally, two follow-up HRCT scans will be performed at both Week 24 (Visit 5) and Week 48 (Visit 7). However, if local IRB approves only one follow-up HRCT timepoint, then the HRCT scans should be collected at Week 0 (Visit 2) and Week 48 (Visit 7). Details regarding image acquisition will be provided in the imaging manual.

4.5.12 Hyperpolarized ^{129}Xe MRI

^{129}Xe MRI will be performed at each study visit as indicated in the schedule of activities (see [Appendix 1](#)). Details for standardization of image acquisition will be provided in the imaging manual.

To confirm that the ^{129}Xe MRI image acquisition procedure has been harmonized across all clinical research sites, approximately 2 volunteers will be tested at each site prior to randomizing the first patient with COPD. Each volunteer will complete two MRI test sessions within an 8-hour timeframe. The test scans from the volunteers will be analyzed centrally per the study-specific imaging manual. Details regarding test scans will be provided in the imaging manual.

Patients and volunteers will be monitored by a qualified medical professional for the duration of the ^{129}Xe dose and post-procedural period, as well as during the MRI.

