4.1.2 Exclusion Criteria

Patients who meet any of the following criteria will be excluded from study entry:

- History of allergy or hypersensitivity to azithromycin
- Significant known respiratory disorders other than COPD that, in the view of the investigator, will affect the trial
- A COPD exacerbation and/or pneumonia within the 4 weeks prior to screening (Visit 1)
- FEV₁ percent predicted less than 25%
- Pregnant or breastfeeding, or intending to become pregnant during the study period (all patients) or within 28 days after the final dose of azithromycin (patients enrolled in Cohort A receiving azithromycin)

Women of childbearing potential must have a negative serum pregnancy test result at screening.

- Participation in an interventional clinical trial within 4 weeks of screening (Visit 1) or receipt of any investigational medicinal product (IMP) within 30 days or 5 half-lives, whichever is longer
- Use of systemic corticosteroids within 4 weeks (oral or IV) or 12 weeks (intramuscular [IM]) prior to screening
- Active tuberculosis requiring treatment within 12 months prior to Visit 1

Patients who have completed treatment for tuberculosis at least 12 months prior to Visit 1 and have no evidence of recurrent disease are permitted.
- Receiving treatment considered to be palliative (life expectancy <12 months)
- Myocardial infarction, unstable angina, or stroke within 12 months prior to screening (Visit 1)
- Clinically significant ECG changes, which in the opinion of investigator warrants further investigation or with a QTc interval > 450 ms
- History of congenital or documented QT prolongation
- Currently receiving treatment with other active substance at doses known to prolong QT interval such as antiarrhythmic of Classes Ia and III, cisapride, and terfenadine
- Electrolyte disturbance (e.g., clinically significant hypokalemia or hypomagnesemia)
- Clinically relevant bradycardia, cardiac arrhythmia, or severe cardiac insufficiency
- History of myasthenia gravis
 - For patients in Cohort A: Known *significant hearing impairment as indicated by a score of ≥ 26 on the Hearing Handicap Inventory in the Elderly—Screening Questionnaire (HHIE-S) or as determined by the investigator*
- Impaired hepatic function
- Severe renal insufficiency (estimated glomerular filtration rate [eGFR] <10 mL/min)
- Concomitant use of ergot derivatives
- Bloodborne infection (e.g., HIV, hepatitis B or C)
- History of *Clostridium difficile* (*C. difficile*) diarrhea

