4.5.15 Six-Minute Walk Test

The 6MWT will be conducted as per the study 6MWT procedural manual that is based on the 2002 ATS guidelines for the 6MWT (ATS Statement 2002).

For safety reasons, all patients should be clinically stable prior to performing any study-related 6MWT. Supplemental oxygen flow rate will be recorded before every

6MWT. Heart rate, SpO₂, and the Borg Category-Ratio 10 (CR10) Scale[®] (Appendix 6) will be recorded immediately before and after the procedure. The Borg CR10 Scale is a 1-item assessment that can be used to measure a variety of perceptions and experiences (i.e., perceived exertion, chest pain, dyspnea, and fatigue) (Borg and Borg 2010). The Borg CR10 Scale ranges from 0 (Nothing at all) to 10 (Absolute maximum/Highest possible).

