- ^r Includes sodium, potassium, chloride, bicarbonate, glucose, BUN, creatinine, calcium, phosphorus, magnesium, total and direct bilirubin, total protein, albumin, ALT, AST, LDH, alkaline phosphatase, creatine phosphokinase, and uric acid.
- ^s If clinically indicated as determined by the investigator. Includes dipstick (pH, specific gravity, glucose, protein, ketones, blood) and microscopic examination (which may include sediment, RBCs, WBCs, casts, crystals, epithelial cells, bacteria).
- ^t Pre-bronchodilator spirometry. Except for Visit 1, patients must withhold inhaled bronchodilator use within the specified window (see Section [4.5.9](#)). The pre-bronchodilator spirometry measurements should not be performed during the screening visit (Visit 1) if the patient did not withhold bronchodilator medications during the specified time period prior to the screening assessment. For safety reasons, spirometry may be omitted if the patient is having an acute COPD exacerbation event at the time of the scheduled visit.

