Appendix 1: Schedule of Activities

- ^u *Sites should ensure that the patient receives a bronchodilator (either daily SOC medication or short-acting bronchodilator on visits where pre-bronchodilator spirometry is performed) prior to performing the ¹²⁹Xe MRI assessment.*
- ^v A chest X-ray must be performed or scheduled at Visit 1 unless a chest X-ray or CT scan has been obtained within 6 months prior to Visit 1 and is available for review by the investigator. The X-ray may be performed locally but must be reviewed by the investigator prior to randomization at Visit 2. If a chest X-ray (or CT scan) is not available in the 6 months preceding Visit 1 or a chest X-ray cannot be completed during screening, the patient will not be eligible for the study.
- ^w An HRCT should be performed at baseline (Visit 2) unless an acceptable set of inspiratory and expiratory scans have been performed within 6 months of screening per imaging manual guidelines. Follow-up sets of scans at Weeks 24 and 48 will be performed as indicated in the SOA if acceptable by site IRB; if determined to be unacceptable by site IRB, a single follow-up set of scans at Week 48 is acceptable.
- ^x For safety reasons, the 6MWT may be omitted if the patient is unable or unwilling to perform the test. Heart rate, SpO₂, and the Borg CR10 Scale ([Appendix 6](#)) will be recorded immediately before and immediately after the procedure.
- ^y Sputum induction will be performed per the study procedure manual. Subjects will be pre-medicated with a bronchodilator and then inhale an aerosolized saline solution delivered by an ultrasonic nebulizer to facilitate forcible coughs and sputum expectoration. Peak expiratory flow and FEV₁ will be monitored during sputum induction for safety. Induced sputum will be processed immediately according to the lab manual at the clinical sites to obtain raw and sputolysin treated sputum samples, as well as sputum cell pellets prepared in a special RNA-protecting solution.
- ^z Blood samples for DNA are optional and should only be obtained from patients who provide written informed consent to participate.

^{aa} The investigator will ask directed questions to assess whether the patient has required any urgent COPD-related health care since the last study visit. Urgent COPD-related health care utilization includes any hospitalizations, emergency department visits, and acute care visits (i.e., unplanned clinic visits). See Section [4.5.14](#) for additional details.

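### The protocol has no rule or analysis for a xenon MRI done during or shortly after an exacerbation, so a temporary VDP rise can create or inflate the primary association

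*Combined protocol and SAP*

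**What the plan says.** **MRI.** Protocol 4.5.12 states that the "MRI will be performed at each study visit as indicated in the schedule of activities". The only patient-state condition is in Appendix 1, footnote u: "Sites should ensure that the patient receives a bronchodilator" before the scan. Section 4.5.12 also states: "Details for standardization of image acquisition will be provided in the imaging manual".

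**Other tests at the same visits.** Footnote t: "For safety reasons, spirometry may be omitted if the patient is having an acute COPD exacerbation event at the time of the scheduled visit". Section 4.5.15: "For safety reasons, all patients should be clinically stable prior to performing any study-related 6MWT". Footnote x adds that "the 6MWT may be omitted if the patient is unable or unwilling to perform the test".

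**Entry.** Section 4.1.2 excludes patients with an exacerbation or pneumonia in the 4 weeks before Visit 1. The baseline scan is at Visit 2, and screening runs from Day -28 to Day -1.

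**Analysis.** The primary endpoint (2.1.1) sets VDP change from baseline to Week 24 against the moderate or severe exacerbation rate over 48 weeks. Section 6.4.1 names a negative binomial model controlling for treatment, and runs sensitivity analyses only if the primary analysis finds a signal. The secondary endpoint (2.1.2) sets VDP change against pre-bronchodilator FEV1 change at Weeks 24 and 48.

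**The concern.** The primary question is whether a change in VDP carries information about exacerbations. If VDP worsens temporarily around an exacerbation, patients who exacerbate often are more likely to be scanned in that state. The event that raised the scan value is also in the 0-48 week count. A positive VDP coefficient can then appear even if stable-state VDP says nothing about exacerbation risk, and a real association can be inflated. Adjusting for treatment does not remove this.

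The VDP-FEV1 comparison has a related problem. Spirometry may be skipped during an acute exacerbation but the scan has no such provision, so FEV1 may be missing at visits where VDP is temporarily raised.

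**Working it through.** **1. The plan's own figure.** The only nearby figure is 77% power for the azithromycin effect (6.1). No power is given for the VDP-exacerbation association. Inputs: mean 2 events over 48 weeks, rate ratio 0.65, one-sided 5%, over-dispersion 1.3, 100 patients 1:1, 10% dropout. Power = Phi(|ln 0.65|/SE - 1.645).
- Reading 1.3 as a variance-to-mean ratio, 50 per arm: SE² = 1.3/(50×2) + 1.3/(50×1.3) = 0.033, SE = 0.182, power = Phi(0.431/0.182 - 1.645) = 76.6%. This matches.
- Same reading, 45 per arm: 72.7%.
- Reading 1.3 or 1/1.3 as the negative binomial dispersion k, 45 per arm: 43% or 53%.

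The point below does not depend on the 77%. Because the meaning of 1.3 is unclear, k = 1.3 and k = 1/1.3 are both used.

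**2. How many Week 24 scans are exposed.** For a window of d days, the mean count is m = (48-week mean) × d/336, and P(at least one event) = 1 - (1 + k·m)^(-1/k).
- 28 days: m = 2×28/336 = 0.167 (SOC) and 1.3×28/336 = 0.108 (azithromycin).
- k = 1.3: 14.0% and 9.6%, average 11.8%. k = 1/1.3: 14.5% and 9.9%, average 12.2%.
- So about 12%, or 11 of 90 evaluable patients. The same formula gives about 6-7% for 14 days and 17% for 42 days.

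**3. False association.** Simulation: 90 patients 1:1, gamma frailty with the two k values, event times uniform, and VDP change standard normal and unrelated to exacerbation risk. A rise is added if an event fell in the window before the Week 24 scan. Negative binomial regression of the 0-48 week count on treatment and VDP change, two-sided 5% Wald test. The size and duration of the rise are assumptions; the documents give neither. With no rise, the test rejects 5-6%.

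| Duration of rise | 0.5 SD | 1 SD | 2 SD |
|---|---|---|---|
| 14 days | 7-8% | 10-13% | 20-27% |
| 28 days | 7-13% | 21-25% | 45-57% |
| 42 days | 12-15% | 33-40% | 73-78% |

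Ranges cover both k values and, for 14 and 28 days, repeated runs. Monte Carlo error is about 1 point near 5% and 2 points near 25%. For a 28-day rise, the spurious rate ratio per SD of VDP change is about 1.08-1.09, 1.14-1.19 and 1.21-1.28 across the columns.

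**4. What changes it (1 SD rise).**
- Counting only events after Week 24: 9-13% (28 days) or 6-8% (14 days).
- Leaving out scans within 28 days after an event: 5-6% (28-day rise).
- Baseline scans contaminated to the same degree (28-day rise): 7-10%.

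**5. Cost of leaving scans out.** With a true rate ratio of 1.35 per SD and no acute rise, the all-scan model recovers 1.35 with power 54-64%. Leaving out flagged scans gives 1.28-1.30 with power 35-44%, because it removes patients on account of outcome events.

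**The case against.** The strongest reply has five parts.

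**The contrast with other tests is limited.** A reader might infer that spirometry and the 6MWT are protected through recovery and only the MRI was overlooked. The documents do not support that. Both provisions are for safety. Footnote t is permissive and covers only an exacerbation present at the visit. Section 4.5.15 asks for clinical stability without naming exacerbations. Neither covers the period just after an event. What stands is that the MRI has no provision at all.

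**A rule may exist elsewhere.** Scan conduct is deferred to the imaging manual, and analysis detail to the SAP cited in 6.4.1. Neither text was available, so the finding is about the protocol text only.

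**The size is assumed.** Both the size and the duration of the rise are assumptions, and a small, short rise does little. The simulation also ignores any effect of the pre-scan bronchodilator or of exacerbation treatment. This stands, and is why a range is shown.

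**Part of it is window overlap.** Much of the effect comes from counting Weeks 0-24 in the outcome. A post-Week 24 count reduces it, nearly to nominal for a 14-day rise. It does not remove it for a 28-day rise, because a recent event also marks an exacerbation-prone patient.

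**Baseline works the other way.** An exacerbation before the baseline scan would push the association down. The route is narrow: 4.4.2 prohibits systemic corticosteroids above 10 mg/day during screening, which leaves mainly antibiotic-only events between Visits 1 and 2.

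**Conclusion.** The point holds for the protocol text. It sets no condition on a scan done during or shortly after an exacerbation and describes no analysis for one, while the primary model counts the same event in the outcome. About 12% of Week 24 scans would fall within 28 days after an event at the plan's rates. With no true link, false rejection runs from near nominal (about 7-8% for 0.5 SD over 14 days) to 45-57% (2 SD over 28 days), and higher still if the rise lasts longer. The central case of 1 SD over 28 days gives 21-25%. These figures rest on an assumed rise and on clean baseline scans.

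Two stronger conclusions are not supported. The documents do not show that an observed association would be spurious, since they give no size for the acute effect. Nor does the problem justify replacing the primary analysis with one restricted to stable scans, which weakens a real association. The distortion of the VDP-FEV1 comparison is plausible but has not been quantified.

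**What to change.** Keep the all-scan model as primary. In the SAP:

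- Derive days since last exacerbation for the baseline and Week 24 scans (and the Week 48 scan for the secondary comparison), using the diary dates and dedicated eCRF in 4.5.13.
- Flag scans during, or within a prespecified interval after, an exacerbation (for example 28 days).
- Prespecify a sensitivity analysis that leaves out flagged scan pairs, for the primary model with the 0-48 week count, the same model with the Week 24-48 count, and the VDP-FEV1 comparison. Report it beside the all-scan result.
- Run it whatever the primary result, as an exception to the rule in 6.4.1, because baseline contamination could also hide a signal.

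The cost is SAP wording, with no new data collection. About 12% of pairs are left out, and up to about 24% if baseline scans were equally exposed. The SAP should state that this analysis attenuates a true association (about 1.35 to 1.28-1.30) and loses power, so it is a sensitivity analysis and not a replacement.

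Whether scans are performed or moved during an exacerbation is for the sponsor to decide, by reconciling 4.5.12 and footnote u with footnote t and 4.5.15. This affects the ±7-day Week 24 window and the same-day assessments and randomization at Visit 2.
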